2.4 Design Rationale

This is a phase 2, non-randomized, single-arm study. The rationale behind the phase 2 design is two-fold. First, a phase 1 dose-escalation study of cobimetinib as monotherapy in cancer patients was previously completed and established the MTD and optimal dosing schedule

(60mg daily; 21/7) as described above²⁴. This cobimetinib dosing schedule was demonstrated to be safe and very efficacious (89% ORR) in a phase 2 study of 18 patients with histiocytic neoplasms, 83% of whom exhibited RAS-pathway activating mutations²⁵. Second, a previous phase 1/2 dose-escalation, nonrandomized trial of the MEK inhibitor trametinib in RAS-mutated AML patients, and a small cohort of CMML patients (n=11) established that single-agent MEK inhibition is safe in patients with leukemia, including CMML²⁶. A subsequent study has confirmed the safety of MEK inhibitors as monotherapy in AML²⁷.

The primary endpoint is objective response rate as per the 2015 MDS/MPN-IWG criteria. The null hypothesis is a response rate of 10% in HMA-treated patients and 35% in newly diagnosed patients. The response rate of 35% in newly diagnosed patients is based on historical response rates with frontline HMA therapy in CMML patients¹. As second-line therapies for CMML do not exist, we would regard a response rate of 10% as standard-of-care for patients who have failed HMA therapies. Simon's two-stage design (Simon, 1989) will be used for both cohorts.

CMML patients comprise an elderly population and often have additional medical comorbidities that limit their activity. CMML patients with an ECOG performance status ≤ 3 are eligible to enroll in this trial. The decision was made to include patients with an ECOG PS of 3 to increase external validity and mimic real-world treatment conditions.

3 DRUG INFORMATION

3.1 Cobimetinib

Cobimetinib is a reversible inhibitor of mitogen-activated protein kinase (MAPK)/extracellular signal-regulated kinase 1 (MEK1) and MEK2. MEK proteins are upstream regulators of the extracellular signal-related kinase (ERK) pathway, which promotes cellular proliferation.

3.1.1 Pharmacology

The pharmacokinetics of cobimetinib was studied in healthy subjects and cancer patients. Cobimetinib exhibits linear pharmacokinetics in the dose range of 3.5 to 100 mg (i.e., 0.06 to 1.7 times the recommended dosage). Following oral administration of 60 mg once daily, steady-state was reached by 9 days with a mean accumulation ratio of 2.4-fold (44% CV).

Absorption: Following oral dosing of 60 mg once daily in cancer patients, the median time to achieve peak plasma levels (T_{max}) was 2.4 (range:1–24) hours, geometric mean steady-state AUC_{0-24h} was 4340 ng·h/mL (61% CV) and C_{max} was 273 ng/mL (60% CV). The absolute bioavailability of cobimetinib was 46% (90% CI: 40%, 53%) in healthy subjects. A high-fat meal (comprised of approximately 150 calories from protein, 250 calories from carbohydrate, and 500–600 calories from fat) had no effect on cobimetinib AUC and C_{max} after a single 20 mg cobimetinib was administered to healthy subjects.

Distribution: Cobimetinib is 95% bound to human plasma proteins in vitro, independent of drug concentration. No preferential binding to human red blood cells was observed (blood to plasma ratio of 0.93). The estimated apparent volume of distribution was 806 L in cancer patients based on a population PK analysis.

[figure not shown]
Elimination: Following oral administration of cobimetinib 60 mg once daily in cancer patients, the mean elimination half-life ($t_{1/2}$) was 44 (range: 23–70) hours and the mean apparent clearance (CL/F) was 13.8 L/h (61% CV).

Metabolism: CYP3A oxidation and UGT2B7 glucuronidation were the major pathways of cobimetinib metabolism in vitro. Following oral administration of a single 20 mg radiolabeled cobimetinib dose, no oxidative metabolites >10% of total circulating radioactivity were observed.

Excretion: Following oral administration of a single 20 mg radiolabeled cobimetinib dose, 76% of the dose was recovered in the feces (with 6.6% as unchanged drug) and 17.8% of the dose was recovered in the urine (with 1.6% as unchanged drug).

3.1.2 Physical and Chemical Properties

Cobimetinib fumarate is a kinase inhibitor. The chemical name is (S)-[3,4-difluoro-2-(2-fluoro-4-iodophenylamino)phenyl] [3-hydroxy-3-(piperidin-2-yl)azetidin-1-yl]methanone hemifumarate. It has a molecular formula $C_{46}H_{46}F_6I_2N_6O_8$ ($2 C_{21}H_{21}F_3IN_3O_2 C_4H_4O_4$) with a molecular mass of 1178.71 as a fumarate salt. Cobimetinib fumarate has the following chemical structure:

3.1.3 Pharmaceutical Properties and Formulation

Cobimetinib is a fumarate salt appearing as white to off-white solid and exhibits a pH-dependent solubility. The inactive ingredients are **Tablet Core:** microcrystalline cellulose, lactose monohydrate, croscarmellose sodium, magnesium stearate. **Coating:** polyvinyl alcohol, titanium dioxide, polyethylene glycol 3350, talc.

3.1.4 Clinical Safety:

The safety and efficacy of cobimetinib were established in a multicenter, randomized (1:1), double-blinded, placebo-controlled trials conducted in 495 patients with previously untreated, BRAF V600 mutation-positive, unresectable or metastatic, melanoma. The presence of BRAF V600 mutation was detected using the cobas® 4800 BRAF V600 mutation test. All patients received vemurafenib 960 mg orally twice daily on days 1–28 and were randomized to receive cobimetinib 60 mg or matching placebo orally once daily on days 1–21 of an every 28-day cycle. Randomization was stratified by geographic region (North America vs. Europe vs. Australia/New Zealand/others) and disease stage (unresectable Stage IIIc, M1a, or M1b vs. Stage M1c). Treatment continued until disease progression or unacceptable toxicity. Patients randomized to receive placebo were not offered cobimetinib at the time of disease progression. The major efficacy outcome was investigator-assessed progression-free survival (PFS) per RECIST v1.1. Additional efficacy outcomes were investigator-assessed confirmed objective response rate, overall

survival, PFS as assessed by blinded independent central review, and duration of response. The median age of the study population was 55 years (range 23 to 88 years), 58% of patients were male, 93% were White and 5% had no race reported, 60% had stage M1c disease, 72% had a baseline ECOG performance status of 0, 45% had an elevated baseline serum lactate dehydrogenase (LDH), 10% had received prior adjuvant therapy, and <1% had previously treated brain metastases. Patients with available tumor samples were retrospectively tested using next-generation sequencing to further classify mutations as V600E or V600K; test results were obtained on 81% of randomized patients. Of these, 86% were identified as having a V600E mutation and 14% as having a V600K mutation.

Use in specific populations:

Pregnancy: Based on findings from animal reproduction studies and its mechanism of action, cobimetinib can cause fetal harm when administered to a pregnant woman. There are no available data on the use of cobimetinib during pregnancy. In animal reproduction studies, oral administration of cobimetinib in pregnant rats during organogenesis was teratogenic and embryotoxic at exposures (AUC) that were 0.9 to 1.4-times those observed in humans at the recommended human dose of 60 mg. Advise pregnant women of the potential risk to a fetus. In the U.S. general population, the estimated background risk of major birth defects and miscarriage in clinically recognized pregnancies is 2–4% and 15–20%, respectively.

Animal Data: Administration of cobimetinib to pregnant rats during the period of organogenesis resulted in increased post-implantation loss, including total litter loss, at exposures (AUC) of 0.9–1.4 times those in humans at the recommended dose of 60 mg. The post-implantation loss was primarily due to early resorptions. Fetal malformations of the great vessels and skull (eye sockets) occurred at the same exposures.

Lactation: There is no information regarding the presence of cobimetinib in human milk, effects on the breastfed infant, or effects on milk production. Because of the potential for serious adverse reactions in a breastfed infant, advise a nursing woman not to breastfeed during treatment with cobimetinib and for 2 weeks after the final dose.

Hepatic Impairment: Pharmacokinetics of cobimetinib has not been studied in patients with moderate or severe hepatic impairment. Dose adjustment is not recommended for patients with mild hepatic impairment (total bilirubin less than or equal to ULN and AST greater than ULN or total bilirubin >ULN but ≤ 1.5 times ULN and any AST) based on results of the population pharmacokinetic analysis.

Renal Impairment: No dedicated pharmacokinetic trial in patients with renal impairment has been conducted. Dose adjustment is not recommended for mild to moderate renal impairment (CL_{cr} 30 to 89 mL/min) based on the results of the population pharmacokinetic analysis. A recommended dose has not been established for patients with severe renal impairment.

4 STUDY DESIGN

4.1 Description

This is an open-label, nonrandomized phase 2 trial to assess the efficacy of cobimetinib in RAS pathway activated CMML. Two cohorts of patients will be accrued using Simon's two-stage design (Simon, 1989) for both cohorts. Cohort 1 will enroll nine newly diagnosed patients in the first stage and if four or more responses are observed five additional patients will be enrolled in the second stage. Cohort 2 will enroll six HMA refractory patients in the first stage and if one or more responses are observed then nine additional patients will be enrolled in the second stage. Study treatment safety will be periodically monitored for excessive toxicity as described in Section 11.3.

Table 2: Cohort Enrollment

Cohort	Stage 1 (n)	Stage 2 (n)
Cohort 1: Newly Diagnosed	9	5
Cohort 2: HMA Refractory	6	9

All eligible patients will be treated daily with cobimetinib in 28-day cycles. Cobimetinib will be administered consecutively for three weeks followed by a one week break prior to the start of the following cycle. Patients will remain on study therapy until treatment discontinuation criteria is met.

Due to discontinuation of cobimetinib supply from the benefactor, study participants who are currently on treatment will discontinue study cobimetinib early under Amendment 6 (v.09DEC2025). These subjects will discontinue treatment and proceed to EOT and Follow-Up.

4.2 Number of Patients

Cohort 1 (newly diagnosed) will enroll N=14 patients. Cohort 2 (HMA refractory) will enroll N=15 patients. The total number of patients on study will be N=29.

4.3 Number of Study Centers

This is a multisite study to be conducted at the Huntsman Cancer Institute at the University of Utah, Salt Lake City, Utah. Up to 2 additional sites may be included.

4.4 Study Duration

From the first patient on trial to completion of the last patient's final follow-up, the trial duration is expected to be 60 months.

5 ELIGIBILITY CRITERIA

This eligibility checklist is used to determine patient eligibility and filed with the enrolling investigator's signature in the patient research chart.

Patient No. _____

Patient's Initials: (L,F,M) _____

5.1 Inclusion Criteria

Yes/No (Response of "no" = patient ineligible)

5.1.1 _____ Male or female subject aged ≥ 18 years.

5.1.2 _____ Untreated or hypomethylating agent (HMA) refractory chronic myelomonocytic leukemia (CMML-1/-2; 2022 WHO classification) with RAS pathway activation as determined by standard-of-care hematopoietic cell sequencing results on peripheral blood or bone marrow demonstrating NRAS, KRAS, PTPN11, FLT3, CBL, JAK2, BRAF or NF1 mutations at a variant allele frequency $\geq 5\%$. BMBx, NGS, FISH or BCR-ABL1 PCR, and cytogenetics should be done at the primary trial site within 21 days prior to C1D1. Results from a previous NGS panel completed within 60 days of registration may be used for the purpose of confirming eligibility.

If the patient is FLT3-ITD positive, the FLT3-ITD PCR allelic ratio must be ≥ 0.05 on testing done on screening biopsy (NOTE: cannot quantitate FLT3-ITD VAF by NGS, must be a separate PCR test).

5.1.3 _____ ECOG Performance Status ≤ 3 .

5.1.4 _____ Adequate organ function as defined as:

- Hepatic:
 - Total Bilirubin $\leq 1.5 \times$ institutional upper limit of normal (ULN)
 - Unless elevation is related to Gilbert's syndrome, hemolysis, or thought to be due to leukemic hepatic involvement.
 - AST(SGOT)/ALT(SGPT) $\leq 3 \times$ institutional ULN
 - Unless elevation is related to leukemic hepatic involvement.
- Renal:
 - Serum creatinine $\leq 2 \times$ ULN

OR

- Estimated creatinine clearance ≥ 30 mL/min by Cockcroft-Gault formula:

- Males: $\frac{(140 - \text{age}) \times \text{weight}[\text{kg}]}{\text{serum creatinine} \left[\frac{\text{mg}}{\text{dL}} \right] \times 72}$
- Females: $\left(\frac{(140 - \text{age}) \times \text{weight}[\text{kg}]}{\text{serum creatinine} \left[\frac{\text{mg}}{\text{dL}} \right] \times 72} \right) \times 0.85$

5.1.5 _____ Left ventricular function $\geq 50\%$ as assessed by echocardiogram or multigated acquisition scan (MUGA)

5.1.6 _____ Negative pregnancy test for women of childbearing potential or evidence of post-menopausal status. Women will be considered post-menopausal if they have been amenorrheic for 12 months without an alternative medical cause. The following age-specific requirements apply:

- Women <50 years of age would be considered post-menopausal if they have been amenorrheic for 12 months or more following cessation of exogenous hormonal treatments and if they have luteinizing hormone and follicle-stimulating hormone levels in the post-menopausal range for the institution or underwent surgical sterilization (bilateral oophorectomy or hysterectomy).
- Women ≥ 50 years of age would be considered post-menopausal if they have been amenorrheic for 12 months or more following cessation of all exogenous hormonal treatments, had radiation-induced menopause with last menses >1 year ago, had chemotherapy-induced menopause with last menses >1 year ago, or underwent surgical sterilization (bilateral oophorectomy, bilateral salpingectomy or hysterectomy).

5.1.7 _____ Highly effective contraception for both male and female subjects throughout the study and at least 3 months after the last dose of study therapy as described in Section 7.4.

5.1.8 _____ Recovery to baseline or Grade ≤ 1 CTCAE v5.0 from toxicities related to any prior treatments, unless AE(s) are clinically nonsignificant and/or stable on supportive therapy.

5.1.9 _____ Able to provide informed consent and willing to sign an approved consent form that conforms to federal and institutional guidelines.

5.2 Exclusion Criteria

Yes/No (Response of “yes” = patient ineligible)

5.2.1 _____ Previous exposure to experimental MEK inhibitors for CMML.

- 5.2.2** _____ Grade 2 or greater QTcF prolongation on screening electrocardiogram (ECG) or clinically significant cardiovascular disease (uncontrolled or symptomatic atrial arrhythmias, congestive heart failure, myocardial infarction/CABG/PCI within 6 months of screening, uncontrolled arterial hypertension or history of ventricular arrhythmia)
- 5.2.3** _____ Clinical or laboratory evidence of central nervous system (CNS) leukemia.
- 5.2.4** _____ Major surgery within 4 weeks prior to study drug initiation.
- 5.2.5** _____ History of interstitial lung disease or pneumonitis.
- 5.2.6** _____ History of retinal detachment, central serous retinopathy (CSR), retinal vein occlusion (RVO), or at high risk for CSR or RVO following screening ophthalmologic exam at discretion of PI/Sub-I following review of exam findings, and, if necessary, consultation with ophthalmology provider.
- 5.2.7** _____ Patients with muscular and/or neuromuscular disorders associated with elevated CPK (e.g. inflammatory myopathies, muscular dystrophy, amyotrophic lateral sclerosis, or spinal muscular atrophy).
- 5.2.8** _____ Any active significant gastrointestinal dysfunction as determined by the clinical investigator to interfere with the patient's ability to swallow or absorb the study treatment, (i.e refractory nausea and vomiting, malabsorption and external biliary shunt)
- 5.2.9** _____ Pregnant or nursing (lactating) women.
- 5.2.10** _____ On chronic treatment with strong CYP3A inhibitors or patients taking St. John's Wort, carbamazepine, efavirenz, phenytoin, rifampin, and other strong and moderate CYP3A inducers.

5.2.11 _____ Treatment for any other malignancy within 2 years of study enrollment, except for adequately treated basal cell or squamous cell skin cancer, carcinoma in situ of the breast, bladder or cervix, low-grade (Gleason 6 or below) prostate cancer on surveillance with no plans for treatment intervention (eg, surgery, radiation, or castration), prostate cancer that has been adequately treated with prostatectomy or radiotherapy and currently with no evidence of disease or symptoms, or any solid tumor malignancy that has been adequately treated for which there is no evidence of active disease within the last 2 years. Patients with monoclonal gammopathy of undetermined significance (MGUS) are permitted to enroll.

5.2.12 _____ Known HIV infection with a detectable viral load at the time of screening.

Note: Patients on effective antiretroviral therapy with an undetectable viral load at the time of screening are eligible for this trial.

5.2.13 _____ Active infection including tuberculosis (clinical evaluation that includes clinical history, physical examination, and radiographic findings, and TB testing in line with local practice), hepatitis B (known positive HBV surface antigen (HBsAg) result), or hepatitis C. Active, controlled infections that, in the opinion of the PI, do not increase risk or interfere with study participation are allowed with prior medical monitor approval.

Note: Patients with a past or resolved HBV infection (defined as the presence of hepatitis B core antibody [anti-HBc] and absence of HBsAg) are eligible. Patients positive for hepatitis C (HCV) antibody are eligible only if polymerase chain reaction is negative for HCV RNA.

5.2.14 _____ Subjects taking prohibited medications as described in Section 6.3.2. A washout period of prohibited medications for a period of at least 5 half-lives or as clinically indicated should occur before the start of treatment.

5.2.15 _____ Known prior severe hypersensitivity to cobimetinib or any component in its formulations (NCI CTCAE v5.0 Grade \geq 3).

5.2.16 _____ Medical, psychiatric, cognitive, or other conditions that may compromise the subject's ability to understand the subject information, give informed consent, comply with the study protocol or complete the study.

I certify that this patient meets all inclusion and exclusion criteria for enrollment onto this study.

Investigator Signature

Date

Time

5.3 Recruitment Strategies

Potential patients will be identified by Investigators in the setting of their outpatient clinics.

6 TREATMENT PLAN

6.1 Administration Schedule

Cobimetinib is taken on a 28-day cycle. Each dose consists of three 20 mg tablets (60 mg) and should be taken once daily for 21 consecutive days (Days 1 to 21-treatment period); followed by a 7-day break (Days 22 to 28-treatment break). Each subsequent cobimetinib treatment cycle should start after a 7-day treatment break has elapsed.

6.2 Cobimetinib

Cobimetinib is a reversible inhibitor of mitogen-activated protein kinase (MAPK)/extracellular signal-regulated kinase 1 (MEK1) and MEK2. MEK proteins are upstream regulators of the extracellular signal related kinase (ERK) pathway, which promotes cellular proliferation.

6.2.1 How Supplied, Stored, Packaged and Labeled

Cobimetinib will be supplied by Genentech as white, round, film-coated 20 mg tablets for oral administration, debossed on one side with “COB”. Each 20 mg tablet contains 22 mg of cobimetinib fumarate, which corresponds to 20 mg of the cobimetinib free base.

Store at room temperature below 30°C (86°F).

6.2.2 Preparation and Administration

Cobimetinib will be prepared and dispensed by appropriately trained and delegated personnel. Subjects will be provided enough investigational product for a full cycle to self-administer at home. Cobimetinib will be administered orally once daily (every 24 hours \pm 4 hours) without regard for food, proton pump inhibitors, or other acid-reducing agents. Subjects should not take extra medication for any reason nor should they re-administer in the case of vomiting after administration. If a dose is missed outside of the dosing window, the dose should not be made up. If a dose is vomited, treatment should be continued as prescribed the following day and the dose should not be made up.

6.2.3 Accountability and Compliance

Cobimetinib must be requested by submitting an order form directly to the drug depot and will be shipped directly to the investigational site.

The investigator, or a responsible party designated by the investigator, must maintain an adequate record of receipt, distribution, and return of all study drugs in the form of a Drug Accountability Form. Such records must be provided to the drug supplier upon request.

Drug compliance will be recorded by patients on the drug diary (see Appendix 5). A member of the study team will review patient drug compliance at the end of treatment for

each cycle and provide patient re-education as required. At the discretion of the principal investigator, a subject may be discontinued from the trial for non-compliance with study visits or study drug.

Excess or unused study drug should be returned to the investigative site, for accounting and destroyed in accordance with GCP after drug accountability has been performed.

6.3 Concomitant Medications and Therapies

Concomitant medications include any prescription or over-the-counter preparation, including vitamins, dietary supplements, over-the-counter medications, and oral herbal preparations taken during the study. Patients may continue their baseline medication(s) providing that the medications are not prohibited on study. Any diagnostic, therapeutic, or surgical procedure performed during the study period should be recorded, including the dates, description of the procedure(s), and any clinical findings, if applicable.

6.3.1 Allowed Therapy

Any medication which is considered necessary for a subject's welfare is permitted and may be given at the discretion of the investigator. Medications for the treatment of underlying disease and symptomatic treatment of adverse events are permitted. Exceptions are listed in the section below.

Use of Blood Products

During treatment, patients may receive red blood cell (RBC) or platelet transfusions, if clinically indicated, per institutional guidelines. Patients who require repeated transfusion support should be discussed with the Sponsor-Investigator.

Appropriate anti-coagulation is allowed during the study (e.g., low molecular weight heparin, direct factor Xa inhibitors, etc.). Warfarin is allowed during the study provided patients are monitored for INR twice a week during the first two cycles of therapy, then weekly to biweekly thereafter.

Patients may receive supportive care with erythropoietin, darbepoetin, granulocyte-colony stimulating factor or granulocyte macrophage-colony stimulating factor, pegylated growth factors, and platelet stimulatory factors, in accordance with clinical practice or institutional guidelines before entry and throughout the study.

Hydroxyurea use is allowed during screening through C2D28 for cytoreduction in cases of highly proliferative CMML. Patients with WBC \geq 25K/uL must be placed on hydroxyurea (at a minimum dose of 500mg twice daily) and allopurinol 3 days prior to C1D1 as leukemoid reaction and tumor lysis syndrome-like reactions to cobimetinib have been observed in the first week of therapy.

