11.6 Statistical Analyses

11.6.1 Primary endpoint

The primary endpoint is overall response rate according to the 2015 MDS/MPN-IWG criteria. Overall response rate (ORR) will encompass patients achieving a complete remission, complete cytogenetic remission, partial remission, marrow response and clinical benefit as per these criteria.

Simon's two-stage design (Simon, 1989) will be used for both cohorts. In the newly diagnosed patients, the null hypothesis that the true response rate is 0.35 will be tested against a one-sided alternative. In the first stage, 9 patients will be accrued. If there are 3 or fewer responses in these 9 patients, the study will be stopped. Otherwise, 5 additional patients will be accrued for a total of 14. The null hypothesis will be rejected if 7 or more

responses are observed in 14 patients. This design yields a type I error rate of 0.1678 and power of 0.8028 when the true response rate is 0.59.

In the HMA refractory patients, the null hypothesis that the true response rate is 0.10 will be tested against a one-sided alternative. In the first stage, 6 patients will be accrued. If there are 0 responses in these 6 patients, the study will be stopped. Otherwise, 9 additional patients will be accrued for a total of 15. The null hypothesis will be rejected if 3 or more responses are observed in 15 patients. This design yields a type I error rate of 0.1559 and power of 0.8100 when the true response rate is 0.30. Two-sided 90% and 95% exact binomial confidence intervals will be reported separately for the newly diagnosed and HMA refractory patients.

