
 • Requires 1 of the following in the absence of progression or CR/partial response and independent of marrow response (cord blood response must be verified at ≥ 8 wk) to be considered a clinical benefit • Erythroid response: 
 ○ Hgb increase by ≥ 2.0 g/dL ○ TI for ≥ 8 wk for patients requiring at least 4 packed red blood cell transfusions in the previous 8 wk ○ Only red blood cell transfusions given based on physician’s judgment for a pretreatment Hgb of ≤ 8.5 g/dL will count in the red blood cell TI response evaluation^{ll} • Platelet response: 
 ○ Transfusion independence when previously requiring platelet transfusions of at least a rate of 4 platelet transfusions in the previous 8 wk ○ Pretreatment $\leq 20 \times 10^9$/L: increase from $<20 \times 10^9$/L to $>20 \times 10^9$/L and by at least 100% ○ Pretreatment $>20 \times 10^9$/L but $\leq 100 \times 10^9$/L: absolute increase of $\geq 30 \times 10^9$/L^e • Neutrophil response: 
 ○ Pretreatment $\leq 0.5 \times 10^9$/L at least 100% increase and an absolute increase $\geq 0.5 \times 10^9$/L ○ Pretreatment, $>0.5 \times 10^9$/L and $\leq 1.0 \times 10^9$/L At least 50% increase and an absolute increase $\geq 0.5 \times 10^9$/L[†] • Spleen response:

 ○ Either a minimum 50% reduction in palpable splenomegaly of a spleen that is at least 10 cm at baseline or a spleen that is palpable at more than 5 cm at baseline becomes not palpable • Symptom response: 
 ○ Improvement in symptoms as noted by decrease of $\geq 50\%$ as per the MPN-SAF TSS scoring < 20 were not considered eligible for measuring clinical benefit.
Disease Progression
(Combination of 2 major criteria, 1 major and 2 minor criteria, or 3 minor criteria from the lists below)
Major criteria

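### The primary ORR has no rule for erythroid, platelet or neutrophil responses obtained on a newly started or increased growth factor, and its transfusion and 8-week conditions are unclear for such responses

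*Combined protocol and SAP*

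**What the plan says.** Section 11.6.1 defines ORR as complete remission, complete cytogenetic remission, partial remission, "marrow response and clinical benefit as per these criteria". Appendix 3 sets the bar for clinical benefit: "Requires 1 of the following in the absence of progression or CR/partial response and independent of marrow response". The qualifying items are an erythroid, platelet, neutrophil, spleen or symptom response.

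Section 6.3.1 permits the agents that act on three of those five items: "Patients may receive supportive care with erythropoietin, darbepoetin, granulocyte-colony stimulating factor or granulocyte macrophage-colony stimulating factor, pegylated growth factors, and platelet stimulatory factors". The permission covers the time before entry and the whole study, guided by usual practice at the institution. On transfusion it says: "During treatment, patients may receive red blood cell (RBC) or platelet transfusions, if clinically indicated, per institutional guidelines". Table 4 also names erythropoietin and transfusion for anaemia. On hydroxyurea, Section 6.3.1 says: "Hydroxyurea use is allowed during screening through C2D28 for cytoreduction in cases of highly proliferative CMML".

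Sections 11.2, 11.5.1 and 11.6.1 contain no scoring rule for a response that occurs on any of these treatments. Appendix 3 contains some limits:

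- Transfusion independence must last at least 8 weeks on the erythroid line.
- Footnote e asks for normalised counts to persist over at least 8 weeks, with haemoglobin and platelets held without transfusion.
- Footnote e has one cytokine condition, in its sentence on myeloid precursors and monocytes.
- Clinical benefit has a verification clause that reads "cord blood response must be verified at" 8 weeks or more.

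**The concern.** Erythropoiesis-stimulating agents raise haemoglobin, G-CSF and GM-CSF raise neutrophils, and platelet-stimulating factors raise platelets. Each of these counts is also a route to the primary endpoint. Section 11.4 attributes response to the MEK inhibitor, but there is no control arm in which the effect of supportive care would also appear. If a patient starts a growth factor on study, reaches the threshold for that lineage and meets no other criterion, the plan as written scores a cobimetinib response.

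Two drafting faults add to this. The line for a haemoglobin rise of 2.0 g/dL does not itself say that the rise must be transfusion-free. The verification clause refers to cord blood, which has no role in this trial, so its application to clinical benefit has to be inferred.

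What is at stake is the Simon decision in each cohort. Cohort 2 passes stage 1 on a single response in 6 patients and rejects its null on 3 in 15.

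**Working it through.** **Inputs (Section 11.5).** Cohort 1: null rate 0.35; 9 patients in stage 1, stop at 3 or fewer responses; reject at 7 or more of 14. Cohort 2: null rate 0.10; 6 patients in stage 1, stop at 0; reject at 3 or more of 15.

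**Formula.** P(reject | p) = sum over stage-1 counts k above the stopping limit of P(X1 = k) × P(X2 ≥ r − k). Here X1 and X2 are binomial counts in stages 1 and 2, and r is 7 or 3.

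**Reproducing the plan.**

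- Cohort 1 at p = 0.35: k = 4 gives 0.2194 × 0.2352 = 0.0516; k = 5 gives 0.1181 × 0.5716 = 0.0675; k = 6 gives 0.0424 × 0.8840 = 0.0375; k = 7 to 9 adds 0.0112. The sum is 0.1678, as stated. Power at 0.59 is 0.8028, as stated.
- Cohort 2 at p = 0.10: k = 1 gives 0.3543 × 0.2252 = 0.0798; k = 2 gives 0.0984 × 0.6126 = 0.0603; k = 3 to 6 adds 0.0158. The sum is 0.1559, as stated. Power at 0.30 is 0.8100, as stated.

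**Sensitivity.** Let x be the share of patients who would otherwise be non-responders but are scored through a growth-factor or transfusion effect. The documents give no value for x, so the range is an assumption. If the null rate p0 contains no such responses (a second assumption), the scored rate under the null is q = p0 + (1 − p0)x.

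| x | q, cohort 1 | Type I error, cohort 1 | q, cohort 2 | Type I error, cohort 2 |
|---|---|---|---|---|
| 0 | 0.350 | 0.168 | 0.100 | 0.156 |
| 2% | 0.363 | 0.195 | 0.118 | 0.219 |
| 5% | 0.3825 | 0.240 | 0.145 | 0.323 |
| 10% | 0.415 | 0.324 | 0.190 | 0.497 |

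**One responder.** If exactly one stage-2 patient is certain to be scored this way, cohort 1 needs 6 or more among the other 13 patients and cohort 2 needs 2 or more among the other 14, with stage 1 passed as before. The rejection probability under the null is 0.247 and 0.316.

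**Timing of hydroxyurea.** C2D28 is day 56. The first scheduled marrow and symptom assessment, C3D21, is day 56 + 21 = 77. The permitted window therefore closes three weeks before that assessment.

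**The case against.** A reader might infer more than this: that all supportive care is unrestricted and unregulated in scoring, so that any clinical-benefit response is suspect. The documents do not support that.

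- **Transfusion.** Footnote e does not confine its transfusion condition to complete remission. It goes on to say that clinical benefit may arise from the same changes, and its marker is printed on a platelet-response line. The condition arguably reaches clinical benefit. What stands is that the haemoglobin-rise line does not state it.
- **Confirmation.** Eight-week persistence appears in footnote e and in the erythroid transfusion-independence line as well. The cord blood clause itself ends by referring to clinical benefit, so it reads as a slip and not as a missing rule.
- **Hydroxyurea.** It is limited to highly proliferative disease and stops at C2D28. A count rebound from a suppressed baseline is speculative: mandatory use begins at WBC 25K/uL, whereas a neutrophil response requires pretreatment neutrophils of 1.0 × 10⁹/L or less.
- **Spleen and symptoms.** Growth factors are no evident route to either, and a symptom score below 20 does not qualify.
- **Type I error.** It would be wrong to say that the stated errors hold only if such responses never count. They hold at a true ORR of 0.35 or 0.10, however composed. Section 2.4 bases 0.35 on historical HMA response rates. If those already include supportively treated responders to the same extent, nothing is inflated. Section 2.4 gives 0.10 as the sponsor's judgement of standard of care. The documents do not say what either rate contains.
- **Safeguard.** CR + PR is a secondary endpoint to which clinical benefit cannot contribute. However, it is analysed descriptively and does not drive the Simon decision.

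None of this answers the growth-factor gap. The only cytokine condition covers precursors and monocytes, not haemoglobin, platelets or neutrophils.

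**Conclusion.** The concern holds in a limited form. The plan lets a single lineage response count towards the primary endpoint, permits the matching growth factors throughout, and has no rule to separate the two. Its transfusion condition is unclear for the haemoglobin-rise line, and its verification clause needs a correction.

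The size cannot be derived from the documents. Under the two assumptions above (x between 2% and 10%, and null rates free of such responses), type I error would be 0.195 to 0.324 in cohort 1 and 0.219 to 0.497 in cohort 2. Cohort 2 is the more exposed because its rejection threshold is low. If the null rates already include similar responses, the inflation is smaller or absent.

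This should be fixed, but it does not invalidate the design. The stated operating characteristics reproduce, and Appendix 3 already limits part of the problem.

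**What to change.** Change analysis wording only; patient care stays as it is.

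1. In Section 11.6.1, state that an erythroid, platelet or neutrophil response counts only if, through the 8-week verification window, there was no transfusion for that lineage and no start or dose increase of the matching growth factor since baseline. State which date baseline refers to.
2. In Appendix 3, replace the words cord blood response with clinical benefit response.
3. Report, as a sensitivity analysis, ORR without patients whose only response is clinical benefit. Flag responses that overlap hydroxyurea use.
4. Under Amendment 6, treated patients are moving to end of treatment, so some responses may already be scored. If so when the rule is adopted, report ORR under both the current and the restricted scoring, so that the change is visible and cannot be taken for a post hoc choice.

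The cost is small. Table 5 already collects concomitant medications from screening, and Section 6.3 requires therapeutic procedures to be recorded with dates. The team should confirm that transfusion dates and growth-factor start dates and doses can be retrieved. The downside is that a few genuine responders who began a growth factor on study would be scored as non-responders, which lowers power somewhat. Reporting both versions shows how much this matters.
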